# 8.3 Analysis of demographic and baseline characteristics

These analyses will be based on the SAF and DLT populations for Phase I and on PP and ITT populations for Phase IIa.

#### 8.3.1 Demographic and baseline characteristics

The following demographic characteristics at baseline will be listed and summarized by cohorts (Cohort #1, Cohort #-1 and overall) with the following items:

- Country
- Gender
- Race (American Indian or Alaska Native / Asian / Black or African American ...)
- Ethnicity (Hispanic or Latino / Not Hispanic nor Latino / Not collected)
- Age at consent (in years)
- Weight (in kg), Height (in cm) and BMI (in kg/m^2)
- Method of analysis for diagnosis (Histological / Cytological / Other)
- Differentiation of the tumor (Poorly / Moderately / Well differentiated / Not Evaluated)
- Etiology of HCC (HCV / HBV / NASH / ETOH / Other)
- Stage of HCC per BCLC (Stage 0 / Stage A / Stage B / Stage C / Stage D)
- Cirrhosis (Yes/No)
- ECOG performance status (0 / 1 / 2 / 3 / 4)
- Previous Cancer History (Yes/No)

Prior cancer therapy details will be listed and summarized by cohorts (Cohort #1, Cohort #-1 and overall) with the following items:

- Number of patients with previous cancer therapy
- Type of Therapy (Radiotherapy / Surgical resection / Radiofrequency ablation (RFA) / Chemoembolization (TACE) ...)
- Setting (Adjuvant / Neo-Adjuvant / Therapeutic / Palliative / Other)
- Number of procedures / treatments
- Best Overall Response (CR / PR / SD / PD / NE)
- Surgical Resection (Complete / Partial)

The following baseline characteristics will be listed and summarized by cohorts (Cohort #1, Cohort #-1 and overall):

- Child-Pugh scoring: Encephalopathy, Ascites, Bilirubin, Albumin, Prothrombin Time or International Normalized Ratio and Total score
- Vital signs: systolic / diastolic blood pressure (in mmHg), heart rate (in bpm), respiratory rate (in bpm) and temperature (in °C)
- Physical examination results presented by Body System and status (normal / abnormal)
- Medical and surgical history including concomitant diseases (other than the studied disease) presented by SOC sorted by alphabetic order and PT within SOCs sorted by decreasing count according to the overall column.
- Signs and symptoms with CT-CAE grade presented by SOC sorted by alphabetic order and PT within SOCs sorted by decreasing count according to the overall column. "Signs and Symptoms" form of eCRF will be completed during Day 1 visit.
- Electrocardiogram: Overall results (Normal / Abnormal NCS / Abnormal CS)
- Thyroid function: TSH, FT3 and FT4.
- HIV/HBV/HCV (Positive / Negative / Not Done)

## 8.3.2 Concomitant diseases

Concomitant diseases are diseases present at the baseline visit and not listed in the exclusion criteria (eg, hypertension, diabetes).

Concomitant diseases will be included in the Medical History.

#### 8.4 Stratification factors

No stratified analysis is planned in this study.

## 8.5 Protocol deviation summaries

All protocol deviations for enrolled patients will be presented by patient in data listings with a distinction between deviations at inclusion and deviations during the study.

The number of patients with at least one major protocol deviation will be summarized by type and overall with a distinction between deviations at inclusion and deviations during the study. All protocol deviations will be reviewed before database lock during the Data Review Meeting.

#### 8.6 Treatments

The treatment information will be based on the SAF and DLT populations for Phase I and on both PP and SAF populations for Phase IIa.

## 8.6.1 Study treatment

The following information will be listed for each patient who received at least one administration of IMP and will be summarized by Cohort (Cohort #1, Cohort #-1 and overall):

- Total number of Pexa-Vec administrations (Table only)
- Number of administrations of Pexa-Vec
- Number of tumors treated with Pexa-Vec
- Cumulative dose of Pexa-Vec for all tumors (pfu)
- Pexa-Vec relative Dose Intensity (percentage)
- Duration of Pexa-Vec exposure (weeks)
- Total number of Nivolumab infusions (Table only)
- Number of infusion of Nivolumab
- Cumulative dose of Nivolumab (mg)
- Nivolumab relative Dose Intensity (percentage)
- Duration of Nivolumab exposure (weeks)

Another table will summarize the number of cancelled or not done administrations (no administration of IMP) and interrupted administration (IMP not fully administered) for each IMP (Pexa-Vec or Nivolumab) with the main reason of non-treatment or interruption for each IMP.

#### 8.6.2 Prior and Concomitant medications

Prior and Concomitant medications are:

- Medications and/or non-drug therapies taken by the patient during the month before Day 1
  of study treatment (i.e., start of the study treatment), continuing or not after the start of the
  study treatment
- All medications and non-drug therapies taken during the treatment period of the study starting from Day 1 up to 28 days after the last study treatment administration

The prior and concomitant medications will be coded using the WHO Drug Dictionary and will be presented by ATC code and Drug Name. A table with the frequency and percentage of patients with prior and concomitant medications will be displayed by cohort (Cohort #1, Cohort #-1 and overall).

## 8.6.3 End of treatment (EOT) and End of study (EOS) visits

The following information will be listed for each patient and will be summarized by Cohort (Cohort #1, Cohort #-1 and overall):

- Week of end of treatment visit defined as integer part of [Study Day / 7]
- Reason for study treatment withdrawal (Progressive Disease / Clinical progression / Occurrence of an unacceptable AE / Pregnancy / ...)
- Week of end of study visit defined as integer part of [Study Day / 7]

# 8.7 Analysis of efficacy

All the efficacy analyses will be based on the PP population which is the primary dataset and will be analyzed and presented by Cohort (Cohort #1, Cohort #-1 and overall). Efficacy analyses will be repeated for ITT population for Phase IIa and for DLT population for Phase I.

All efficacy variables will be listed in dedicated listings by subject and the following summaries will be presented by Cohort (Cohort #1, Cohort #-1 and overall) in case of de-escalation in any part of the study:

- Continuous efficacy endpoints will be summarized using N, Mean, sd, Median, interquartile range (Q1-Q3), MIN, and MAX. If appropriate, log-normal variable will be log-transformed for descriptive statistics.
- Categorical efficacy endpoints will be summarized using number and percentage (with exact 95% CI).

 Survival efficacy endpoints will be presented using the number of events, number and percentage of censored patients, quartiles (Q1, median and Q3) and the associated 95% CI.
 A graphical representation will be done for these endpoints using a Kaplan-Meier curve with 95% CI.

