#### 1 INTRODUCTION

#### 1.1 Background

#### 1.1.1 Hepatocellular Carcinoma

Hepatocellular carcinoma (HCC) is estimated to be the third most common cause of cancerrelated deaths world-wide (*Ferlay 2010; Hoos 2012*), the 5th most common cancer diagnosis in men worldwide and the 7th most common cancer in women (*El-Serag 2012*).

Approximately 750,000 people develop HCC world-wide each year with ~80% of cases reported in developing countries which have a high prevalence of hepatitis (*El-Serag 2012*). However, HCC is one of the only cancers whose incidence is increasing in developed countries (*Siegel 2014*; *El-Serag 2001*; *Goodgame 2003*; *Deuffic 1998*). Approximately 25,000 new cases of HCC are diagnosed annually in the United States (US) (*Siegel 2014*). The incidence of HCC is 1,550 new cases in Canada (*Canadian Cancer Society 2008*) and approximately 50,000 in Europe (*Ferlay 2013*).

Most HCC cases (approximately 90%) develop in the context of liver disease, in particular hepatocellular cirrhosis (Simonetti 1991; Bosch 1999). The most common causes of cirrhosis include chronic hepatitis B or C, and chemical substances such as excessive alcohol or aflatoxins (Chen 2003). Nonalcoholic steatohepatitis, a liver disease triggered by enhanced fat deposition in the liver, may also be a risk factor for the development of HCC (Hashimoto 2009; Mori 2004). The risk of death from HCC is increased both in males and females with increasing body mass index class, linking obesity to development of HCC (Calle 2003).

Patients with HCC generally present with advanced disease with a poor prognosis of 6 to 9-month median survival (*Yoo 2003*). Therefore, development of effective methods for the prevention and early diagnosis of HCC methods are critical. In addition, there exists a continued need for new therapies that will further improve survival of patients with HCC.

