## 2.1 Phase I

The Phase I part is a single cohort enrolling 6 patients at standard Pexa-Vec and nivolumab doses, i.e.  $1x10^9$  pfu and 240 mg, respectively.

Pexa-Vec will be administered by intra-tumoral infusion on D1, D15 and D29, and nivolumab by intravenous infusion on D15 and D29 and then every two weeks. The study will document dose-limiting toxicities (DLTs) and landmark AEs. A landmark AE is an anticipated effect of the combination defined as an increase in severity of hepatic cytolysis (doubling of AST – ALT baseline blood concentrations), or significant deterioration of hepatic function (INR, bilirubin), or increase in incidence or severity of immune-related AEs, or increase in number or severity of Pexa-Vec-related skin lesions.

The first patient will be monitored for the safety scheduled up to D29, i.e. the end of the DLT monitoring period, before 5 additional patients can be enrolled. In addition, a security time interval of 2 weeks between enrolments of consecutive patients will apply. This time interval is appropriate to prevent additional patients to be exposed to potential acute or subacute toxic events observed in the previous patients.

If more than one DLT is observed in the first 6 patients, or in case of the occurrence of a landmark AE, one de-escalation dose regimen will apply on a cohort of 6 additional patients. Depending on the DLT profile relative to the known toxicity of each component of the combination and upon the recommendation of the Independent Safety Committee (ISC), the doses of Pexa-Vec and nivolumab will be either  $3x10^8$  pfu for Pexa-Vec and 240 mg q2 weeks for nivolumab OR  $10^9$  pfu for Pexa-Vec and 240 mg q3 weeks for nivolumab

In case no more than one DLT and no occurrence of any landmark AE is observed in 6 patients at the initial Phase I dose level or, if relevant, at the de-escalation dose level, the Phase IIa part of the study could start.

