## Per protocol (PP) population

In Phase IIa, patients without major protocol deviations who received at least 2 administrations of Pexa-Vec and 2 administrations of nivolumab and undertaken at least one post-baseline assessment and/or with any evidence of disease progression other than CT scan will be included in PP population. Comparable patients from Phase I (same inclusion/exclusion criteria and same treatment regimen) without major protocol deviation who received at least 2 administrations of Pexa-Vec and 2 administrations of nivolumab and undertaken at least one post-baseline assessment and/or with any evidence of disease progression other than CT scan will also be included in PP population. The patients will be analyzed according to the treatment planned and this dataset will be the primary dataset for efficacy evaluation.

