# Anticipated but not limited major deviations are:

- Failure to complete all 3 IT Pexa-Vec injections and 2 nivolumab IV infusions in the absence of DLT in the Phase I part, 2 IT Pexa-Vec injections and 2 nivolumab IV infusions in the Phase IIa part,
- No histological confirmation of HCC,
- Previous systemic therapy for HCC,
- Child-Pugh score beyond A, or deteriorated hepatic function beyond score, or advanced cirrhosis diagnosis based on albuminemia, INR, bilirubin blood levels and clinical symptoms: uncontrolled ascites or esophageal varices, etc.
- ECOG PS > 1,
- Prohibited concomitant medications or no withdrawal of anti-hypertensive, anticoagulant or anti-platelet medications within protocol-specified conditions,
- Immunodeficiency,
- Pregnancy and breast-feeding.

GCP deviations (including protocol deviations, applicable SOPs deviations etc) must be tracked. Transgene shall be provided with a deviation listing before the data review meeting. The criticality of each deviation will be established in agreement with Transgene during the data review meeting (at the latest) in order to define the different populations for analyses.

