#### 8.7.2 Secondary efficacy endpoints and analyses

The following secondary efficacy endpoints will be considered:

- Disease control rate (DCR) is the proportion of patients whose best overall response is either CR, PR, or SD.
- 4-month (18-week) DCR is proportion of patients whose best overall response is either CR, PR, or SD 4 months after D1 (using tumor assessments before Day 127).
- The Time to Progression (TTP) is the time from Day 1 to the date of first documented radiographic tumor progression. TTP does not include deaths. If a patient has not had a TTP event at the cut-off date for analysis, TTP will be censored at the date of last evaluable tumor assessment before the cut-off.
- Progression Free Survival (PFS) is the time from Day 1 to the date of first documented tumor progression or death due to any cause, whichever occurs first. If a patient has not had a PFS event and is not known to have died at the cut-off date for analysis, PFS will be censored at the date of last evaluable tumor assessment before the cut-off.
- Overall Survival (OS) is the time from Day 1 to the date of death due to any cause. If a
  patient is not known to have died at the cut-off date for analysis, survival will be censored
  at the date of last contact.
- Duration of overall Response (DoR) applies only to patients whose best overall response is CR or PR. The start date is the date of first documented response (CR or PR) and the end date is the date of first documented disease progression or the date of death due to underlying cancer. DoR will be censored if progression or death due to underlying cancer is not observed at the cut-off date for the analysis, or death to another cause than underlying cancer or start of further anti-cancer therapy. The censoring date will be the date of the last

evaluable tumor assessment.

- Tumor size (in mm) is defined as the sum of the diameters recorded for all target lesions as identified at baseline. Relative change from baseline in tumor size over time will be summarized and graphically represented. This value is automatically calculated in "Follow-up target lesions" form of eCRF.
- HBV DNA and HCV DNA viral load (and change from baseline) will be summarized for each visit.

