For OS, the percent survivors over time will also be presented considering the proportions of patients alive at 6, 9, 12, 18, and 24 months, along with corresponding 95% CIs. At these timepoints the restricted mean survival time with 95% CI will be calculated.

For PFS, the percent of non-progressors over time will also be presented considering the proportions of patients having not progressed at 6, 9, 12, 18, and 24 months, along with corresponding 95% CIs. At these timepoints the restricted mean non-progression time with 95% CI will be calculated.

For Tumor size, a graphical representation will be done using a waterfall plot. This plot will display the best percentage change from baseline for each patient, sorted in descending order (using bar) and colored by the Best Overall Response (CR/PR/SD/PD).

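### Overall survival in the primary per-protocol set is counted from Day 1, although membership requires a second nivolumab dose at about D29, so earlier deaths cannot appear and survival is modestly overstated (PFS less so)

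*SAP*

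**What the plan says.** SAP section 8.7 opens with "All the efficacy analyses will be based on the PP population which is the primary dataset". SAP section 6 and Protocol sections 12.3.3 and 12.6 also make the PP set primary for efficacy. SAP 8.7 repeats the Phase IIa efficacy analyses in the ITT set, which SAP 6.1 defines as everyone given at least one dose of either product.

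PP membership in SAP 6.1 is limited to patients without major deviations "who received at least 2 administrations of Pexa-Vec and 2 administrations of nivolumab and undertaken at least one post-baseline assessment". The sentence goes on to allow evidence of progression from a source other than CT, joined by and/or. SAP 6.2 lists as a major deviation the failure to complete "2 IT Pexa-Vec injections and 2 nivolumab IV infusions in the Phase IIa part". The schedule in SAP 2.1 is "nivolumab by intravenous infusion on D15 and D29 and then every two weeks", and SAP 5.2 gives the same start and interval for both parts.

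The clock is set in SAP 7.7.2 and 8.7.2: "Overall Survival (OS) is the time from Day 1 to the date of death due to any cause". PFS has the same origin. Milestone proportions are planned at 6, 9, 12, 18 and 24 months, and for OS "At these timepoints the restricted mean survival time with 95% CI will be calculated". Neither document provides a landmark, delayed entry or other adjustment for the exposure condition.

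**The concern.** Membership of the PP set is decided by something that happens after the clock starts. To receive a second nivolumab dose planned for D29, a patient must be alive on that day. A patient who dies on D20 is not an early event in the primary OS curve. He or she is absent from it and, under Protocol 6.6.2, is replaced. The PP curve is therefore flat at 100% up to the second nivolumab dose, and the median, the milestones and the restricted mean all carry that guaranteed time.

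SAP 7.4 says that DCR, TTP and survival parameters will be considered before concluding that the combination does not merit further exploration. Survival can thus speak in favour of a regimen that has failed on ORR. As written, the survival results presented first come from the favourably conditioned set.

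**Working it through.** **The plan's own figure.** The documents give no sample size, event count or power for OS or PFS. The nearest stated figure is the allowance for non-evaluable patients in SAP 2.3: 42/(1 − 0.10) = 46.7, rounded up to 47. It reproduces.

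**Inputs.**
- Guaranteed time: D29 − D1 = 28 days. With the SAP 7.7.2 conversion of 30.4375 days per month, L = 28/30.4375 = 0.92 months. The ±1 day windows at either end give 26 to 30 days, or 0.85 to 0.99 months.
- Survival scenarios from the Protocol: 62% alive at 12 months on nivolumab alone (1.4.1.1.2); medians of 6.7 and 14.1 months by Pexa-Vec dose (1.4.1.1.1) and 8.5 to 10 months on first-line sorafenib (1.1.2); and the general statement in 1.1.1 of a "poor prognosis of 6 to 9-month median survival", from which 9 months is used.
- Assumption: exponential survival from Day 1.

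**Formula.** Among patients alive at L, S_PP(t) = S(t)/S(L) for t > L. With constant hazard h = ln 2/median this is exp(−h(t − L)), so the PP median is the true median plus L.

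**Medians.** 6.7 becomes 7.62 months (+13.7%), 8.5 becomes 9.42 (+10.8%), 10 becomes 10.92 (+9.2%) and 14.1 becomes 15.02 (+6.5%). A simulation with a 10-month median gave 9.99 for all treated patients, 10.92 for PP counted from Day 1, and 10.00 for PP counted from D29.

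**Milestones.**
- True 12-month OS 62%: h = −ln(0.62)/12 = 0.0398; S(L) = 0.964; 0.62/0.964 = 64.3%.
- Median 9 months, 6-month OS: h = 0.0770; S(6) = 63.0%; S(L) = 0.932; the PP curve reads 67.6%.
- Median 10 months, 12-month OS: 43.5% reads 46.4%.

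**In patients.** In the first two cases, filling 30 PP places takes 30/0.964 = 31.1 and 30/0.932 = 32.2 treated patients. That is about one or two early deaths left out.

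**Without constant hazard.** If q is the share of patients dying before they qualify, S_PP = S/(1 − q). A true 62% reads 62%, 63.3%, 65.3% and 68.9% for q = 0, 2%, 5% and 10%. The last would need the entire planned non-evaluable allowance to be early deaths. If the hazard before L is a fraction r of the later hazard, the median shift is r × L: 0.46 months at one half, 0.23 at one quarter, and zero if no one dies early.

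These figures treat early death as the only way of failing the criterion. Patients who live past D29 but miss a dose are also excluded; that effect is not quantified here.

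**The case against.** The strongest reply is that the unconditioned estimate is already planned. The Phase IIa ITT repeat uses the same endpoint definitions from Day 1, and OS and PFS are descriptive secondary endpoints with no test or threshold. This largely stands, and it is why the remedy is cheap. It does not dispose of the point, because PP is named as primary and no rule says that ITT governs survival.

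Second, entry requires Child-Pugh A, ECOG 0 or 1 and a life expectancy of at least 3 months. Early deaths may well be fewer than a constant hazard implies, and the 6 to 9-month median describes HCC patients in general. This stands too: the figures above are at the upper end. With 30 patients, a 65% milestone has a 95% interval of about ±17 points (1.96 × √(0.65 × 0.35/30) = 0.17), which is much wider than the bias. The bias nevertheless has a fixed direction.

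Third, the and/or in the PP definition might be read as admitting early progressors who missed doses. The major-deviation list in SAP 6.2 excludes them.

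Three stronger readings are tempting, and the documents do not support them:
- A reader might infer that survival to the Week 6 scan is also guaranteed (42/30.4375 = 1.38 months). It is not, because a patient who received the doses and then progressed clinically before that scan still qualifies.
- A reader might infer that PFS is shifted as much as OS. The first scheduled scan is at Week 6 in every set, so the PFS curve is nearly flat until then in ITT as well. What differs is mainly the loss of early deaths and early clinical progressors.
- A reader might infer that PP survival will be formally compared with historical single-agent survival. The documents name no survival comparator; their historical benchmark is for ORR.

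**Conclusion.** The point holds for OS and, to a smaller and unquantified extent, for PFS. The primary PP survival curve excludes deaths before the second nivolumab dose by construction and reads S(t)/S(L). Under constant hazard from Day 1 and L = 0.92 months, median OS is overstated by about 0.9 months and the milestones shown by about 2 to 5 percentage points. Given the entry criteria, that is an upper-end figure: the bias falls in proportion to the early hazard and is zero without early deaths. No type I error is at stake. The change is still worth making, because survival is to be weighed before the combination is abandoned and the plan leads with the set that can only flatter it in this respect.

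**What to change.** In SAP 8.7 and 8.7.2, make the ITT analysis from Day 1 the primary presentation for Phase IIa OS and PFS, covering medians, milestones and restricted means. Label the PP curves as supportive and conditional on receiving the second nivolumab dose. The PP set can stay primary for ORR; this point does not concern it. Because Protocol 12.3.3 and 12.6 also name PP as primary for efficacy, record the departure in the SAP change history.

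If a PP curve for OS is kept, use delayed entry, or a landmark, at each patient's actual second nivolumab date. Do not use entry at the first scan: a patient whose first scan shows progression would have the same entry and event date, contribute no time at risk and be dropped by standard programs, which would overstate PFS.

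The cost is SAP wording and, if the PP curve is kept, an entry-time option in existing programs. No new data or patients are needed. The downside for the sponsor is slightly less favourable survival figures.
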